9.1. Adverse events

Adverse events are common in this population due to the range of underlying comorbidities, therefore events that are deemed expected for this population (see section 9.2.1) will not be reported. Care home staff will report pre-specified adverse events (based on treatments under investigation for any given comparison group within the platform – further details are specified within the relevant IMP appendices) for all residents directly via the eCRF

9.2. Serious adverse events

Care home staff directly involved in the care of participants will report all events that meet the definition of an SAE, other than those events excluded from reporting (listed in section 9.2.1). An SAE is defined as an AE that meets any of the below criteria:

- 1. results in death;
- 2. is life-threatening;
- 3. requires hospitalisation or prolongation of existing hospitalisation;
- 4. results in persistent or significant disability or incapacity; and
- 5. consists of a congenital anomaly or birth defect.

Important medical events that may not result in death, be life-threatening, or require hospitalisation may be considered a serious adverse event when, based upon appropriate medical judgment, they may jeopardize the patient or participant and may require medical or surgical intervention to prevent one of the outcomes listed in this definition.

A distinction is drawn between serious and severe AEs. Severity is a measure of intensity whereas seriousness is defined using the criteria above. Hence, a severe AE need not necessarily be serious.

9.2.1. Events that do not require reporting

The following events are frequent in care homes and will not be reported as AEs or SAEs:

Trial	Prophylactic therapy in care homes trial	Protocol	Final v1.0	date:	13-May-2021	Page:	29 of 44
name:	U1111-1265-4068	version:					

- Agitation
- Allergic reaction (not related to trial medication)
- Anorexia, loss of appetite
- Bowel obstruction
- Bruising, ecchymoses
- Confusion
- COVID-19 (part of the primary outcome)
- Delirium
- Dehydration
- Diarrhoea, with/without norovirus/Clostridium difficile
- Fall with injury, with/without fracture
- Heart failure, volume overload
- Hypoglycaemia
- Hypotension
- Incontinence (urinary, bowel)
- Medication (non-trial) error
- Nursing care, missed
- Pressure ulcer
- Respiratory distress/failure (non-COVID-19)
- Respiratory infection (non-COVID-19)
- Sepsis, bacteraemia
- Skin tear, abrasion, breakdown
- Suicide, attempted suicide, self-harm
- Surgical/procedural site infection
- Urinary tract infection, with/without catheter
- Venous thromboembolism
- Vomiting, with/without norovirus
- Any event listed in the IMP appendices

Similarly, diagnoses present at baseline (including any worsening of that condition) and known comorbidities will not be reported. Known side effects for the intervention(s) will be listed in the relevant IMP appendix.

If any of the above lead to hospitalisation or death, then they will comprise part of the primary outcome.

Trial	Prophylactic therapy in care homes trial	Protocol	Final v1.0	date:	13-May-2021	Page:	30 of 44
name:	U1111-1265-4068	version:					

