9.3. Reporting period

As a minimum, SAEs will be documented and reported in accordance with the procedures described above from the date of first administration of IMP until the end of the IMP treatment period. Any collection of SAEs beyond the treatment period will be specific to the intervention under investigation and the rationale for this will be described within the specific IMP appendix of the protocol. SUSARs must still be reported in an expedited manner irrespective of how long after administration the reaction occurred.

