9.4.2. Serious adverse events

SAEs will be entered into a trial SAE form within the eCRF by a member of care home staff or GP directly responsible for the care of the participant. The person completing the report will include sufficient details of the event to facilitate the assessment of relatedness by a member of the national team of medically qualified Principal Investigators. Should a participant's general practitioner become aware of an SAE during the reporting period, they may report the event via the same process. A Principal Investigator will review the information in the SAE report and will liaise with the reporting care home or GP to obtain further information where necessary.

On receipt of an SAE, seriousness and causality will be determined independently by the PI. An SAE judged by the PI to have a reasonable causal relationship with the trial treatment will be regarded as a SAR. The PI will also assess all SARs for expectedness against the Reference Safety Information for the IMP. If the serious event is unexpected (i.e. is not defined in the protocol as an expected event) it will be classified as an unexpected SAR (SUSAR). Expedited reporting for SUSARs will be carried out as detailed in section 9.5.2.

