8. ANALYSIS OF SAFETY

8.1. Serious adverse events (SAEs)

Safety reporting in the trial will focus only on those events that could be related to the trial medication, are serious in nature (according to the SAE definition in the protocol) and are unexpected (either the event itself or in severity) according to the reference safety information (RSI) for the IMP. Further information regarding the RSI can be found in the appendix in the protocol for the relevant IMP.

Descriptive summaries for each treatment group will be presented to show:

- The number and percentage of residents with at least one SAE and the total number of SAEs.
- The number and percentage of residents with at least one SAR (serious adverse reaction, related to IMP not unexpected), the total number of SARs and number with each event (MedDRA preferred term)
- The number and percentage of residents with at least one SUSAR (Suspected Unexpected Serious Adverse Reaction), the total number of SUSARs and the number with each event

Serious adverse reactions (SARs) and suspected unexpected serious adverse reactions (SUSARs) will be listed by treatment group.

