8.2. Adverse events relevant to the intervention

Adverse events relevant to the intervention as specified in the relevant IMP-specific protocol appendix will be reported on the eCRF by asking care home staff if the resident has experienced the event. These adverse events will be presented descriptively by treatment group for each pairwise comparison.

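### The reporting exemption in Protocol 9.2.1 contradicts the sections that require appendix-listed events, and the by-arm SAE table has no clear common window

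*Protocol*

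**What the plan says.** **Exemption.** Protocol 9.2.1 opens with the rule "The following events are frequent in care homes and will not be reported as AEs or SAEs". It names 27 event types and closes with "Any event listed in the IMP appendices", without qualification. Protocol 9.2 and 9.4.1 make the list operative: staff report SAEs other than those it excludes. The same subsection states: "Known side effects for the intervention(s) will be listed in the relevant IMP appendix".

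**Opposing requirements.** Protocol 9.1 says "Care home staff will report pre-specified adverse events" for all residents and points to the IMP appendices for detail. Protocol 9.4.1 extends this explicitly to standard care. The introduction to Protocol 9 has all side effects entered weekly. Protocol 2.2 makes appendix-specified AEs a safety outcome, and 14.9 has adjudicators classify targeted reactions. SAP 8.2 says "Adverse events relevant to the intervention as specified in the relevant IMP-specific protocol appendix will be reported on the eCRF" and presents them by group. SAP 8.1 tabulates SAEs by group, and also "The number and percentage of residents with at least one SAR (serious adverse reaction, related to IMP not unexpected").

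**Expectedness.** Protocol 9.4.2 assesses SARs against the RSI, but then explains an unexpected event as one that "i.e. is not defined in the protocol as an expected event". Protocol 14.9 uses a similarly wide test.

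**Window.** Protocol 9.3 sets SAE reporting, as a minimum, "from the date of first administration of IMP until the end of the IMP treatment period". Protocol 8.2 lists SAEs and targeted AEs under days 1 to end of treatment, after day 0 (randomisation).

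**The concern.** Care home staff cannot follow both sets of rules. On the literal wording of 9.2.1, events in an IMP appendix leave AE and SAE reporting, although the safety outcome and two SAP tables are built on them. The exemption also acts before anyone judges causality, because under Protocol 9.4.2 the PI assesses relatedness on receipt of an SAE. An event that is never submitted is not assessed by that route.

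Separately, an SAE percentage by arm is interpretable only if residents in each arm are observed over the same period. A window that opens at first dose has no start in standard care.

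Safety through serious adverse reactions is a stated secondary objective, and the DMC reviews these data. Events not reported at the time may be hard to recover later with enough detail to judge causality.

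**Working it through.** The plan gives no figure to reproduce on this point. The check sets the passages side by side, with one count and one illustration.

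**1. Is the exemption compatible with the rest?**

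| Event class | Protocol 9.2.1, read literally | Elsewhere |
|---|---|---|
| Pre-specified AEs detailed in an appendix | Not reported | Reported for all residents, standard care included (Protocol 9.1, 9.4.1); safety outcome (2.2); classified by adjudicators (14.9); tabulated (SAP 8.2) |
| Known side effects listed in an appendix | Not reported | All entered weekly (Protocol 9, introduction) |
| Serious, related, appendix-listed | Not reported as an SAE | Needed for the table of SARs that are not unexpected (SAP 8.1) |

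Each row conflicts.

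**2. How wide is the rest of the list?** It names 27 event types besides the appendix item. Two separate trial from non-trial causes (allergic reaction, medication error). That leaves 27 − 2 = 25 with no carve-out, including sepsis, venous thromboembolism, hypotension and hypoglycaemia.

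**3. Which of these still reach review?** The introduction to Protocol 9 sends hospitalisations and deaths, as well as SAEs, to the PI, the adjudicator and the DMC. Under Protocol 14.9 adjudicators review outcome events. An exempt event that causes admission or death therefore has a route. The gap is a serious event that causes neither: one that is life-threatening, disabling or medically important and is managed in the home. SAP 5.2 and the footnote to SAP Table 1 recognise residents with a directive against hospitalisation, so such events are plausible; the documents do not say how many.

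**4. Do the two tests of expectedness agree?** Protocol 9.5.1 and the introduction to Protocol 9 use the RSI. The gloss in 9.4.2 and the wording in 14.9 refer to events expected under the protocol, and 9.1 describes the 9.2.1 list as events expected in this population. A related serious event that is on that list but absent from the RSI could be unexpected by one test and expected by the other.

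**5. What window does the SAE table use?** Standard care receives no additional intervention, so 9.3 gives it no start date. IMP-allocated residents who are never dosed also have none, yet SAP 4.2 puts safety outcomes in the ITT set. Protocol 8.2 suggests days 1 to end of treatment, but the key to Figure 1 defines end of treatment by trial treatment. SAP 8.1 states no window.

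Illustration. IMP is prescribed, dispensed and shipped after allocation (Protocol 7.1), and the delay d to first dose is not given. Suppose standard care is counted from randomisation to day 42 and IMP homes from day d to day 42. The IMP window is then shorter by d/42:

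- d = 1: 1/42 = 2.4%
- d = 3: 3/42 = 7.1%
- d = 7: 7/42 = 16.7%

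If end of treatment is instead first dose plus 42 days, the windows are equal in length but shifted by d days.

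**The case against.** The strongest reply is that most of the safety evidence survives. Protocol 9.4.1 requires targeted AEs in standard care, and the 9.3 window covers SAEs only. SARs and SUSARs are by definition related to IMP and need no comparator window. All-cause hospitalisation and death are ascertained in every arm for 60 days from randomisation. Section 9.3 says as a minimum, and Protocol 8.2 with the 42-day end of treatment can be read as a common window. All planned safety summaries are descriptive, and the narrow reporting focus is stated openly in Protocol 9.

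All of this stands. It rules out the inference that the safety comparison as a whole cannot work, and the inference that every suspected reaction of an exempt type would be missed.

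A reader might also infer that the SAR table must be empty. That would need the literal reading of 9.2.1 to be the intended one. The item could mean events that an appendix marks as exempt, or it could exempt spontaneous reports while solicited collection continues. The text does not say, and the IMP appendices are not among the documents. Nor can it be assumed that the appendices list the RSI terms; Protocol 9.5.1 says only that the RSI is referred to there.

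What the reply does not remove is the contradiction in wording, the gap before causality review for serious events without admission or death, the double standard of expectedness, and the lack of a stated start for standard care.

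**Conclusion.** The concern holds in a limited form. The appendix item in 9.2.1 contradicts Protocol 2.2, 9, 9.1, 9.4.1 and 14.9 and SAP 8.2, and puts the expected-SAR table in SAP 8.1 at risk. For 25 of the 27 other exempt event types, a serious event without admission or death may escape PI causality review. SUSAR expectedness has two tests. The by-arm SAE percentages have no clear common window; a shortfall of 2.4% to 16.7% in the IMP arm follows only under the assumed delays of 1 to 7 days and a shared day-42 end.

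The number of events affected cannot be estimated from the documents. The primary analysis is not affected. The correction should still be made before a comparison opens, because following the text as written could lose events that the plan's own safety outcome needs, and the remedy is short.

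**What to change.** 1. Protocol 9.2.1: delete the appendix item, or limit it to events that an appendix expressly marks as exempt. Reconcile it with Protocol 9, 9.1 and 9.4.1 and SAP 8.2.
2. Protocol 9.2.1: state that the exemption does not apply to a serious event that staff, GP or PI suspect may be related to IMP. Staff would only flag suspicion; causality stays with the PI as in 9.4.2. This matters because Protocol 1.2.1.1 says 72% of care homes have no registered healthcare professionals in core staffing.
3. Protocol 9.4.2 and 14.9: judge SUSAR expectedness against the RSI only.
4. Protocol 9.3 and SAP 8.1: count SAEs in every arm from randomisation to the same fixed day, at least the planned end of treatment, including residents who are never dosed.

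The cost is a few sentences of protocol amendment, a sentence in the SAP, and some extra SAE reports through the existing eCRF for PI review. The documents give no basis for estimating how many.

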It is expected that participants in the trial will have a range of underlying co-morbidities and so infection with SARS-CoV-2 may lead to serious and significantly life-threatening conditions, which are outcomes for this trial. Safety reporting in the trial will therefore focus only on those events that could be related to the trial medication, are serious in nature (according to the SAE definition below) and are unexpected (either the event itself or in severity) according to the reference safety information (RSI) for the IMP. Further information regarding the RSI can be found in the appendix for each IMP. Once an intervention has been identified by the NIHR Prophylaxis Oversight Group, the risk profile of the IMP will determine any further safety reporting requirements beyond those described below. These will be detailed within the IMP appendix.

Trial	Prophylactic therapy in care homes trial	Protocol	Final v1.0	date:	13-May-2021	Page:	28 of 44
name:	U1111-1265-4068	version:					

The known or anticipated side effects of the IMPs are listed in the IMP appendices. Side effects will be apparent to residents with capacity and to care home staff. In particular, care home staff know their residents and their medical problems intimately and so can see deterioration very early; indeed side effects are likely to be identified earlier and potentially more frequently than they would be in people living in their own home. We will train care home staff to look for side effects through training at the site initiation visit and in videos available for download via the trial website. If side effects are apparent, care home staff may inform the resident's GP. All side effects will be entered into the trial database on a weekly basis by care home staff. Serious adverse events, hospitalisation and death will all be reported in real time via the trial database for review by the relevant principal investigator, for independent review by the medical adjudicator and Data Monitoring Committee, and for forwarding to the competent authority within the standard reporting periods relevant to SAEs, SARs and SUSARs.

A serious adverse event that is not expected against the RSI and considered to be related or suspected to be related to the IMP is classed as a Suspected Unexpected Serious Adverse Reaction (SUSAR) and requires expedited reporting as per the clinical trials regulations.

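### Protocol 9.2.1 exempts listed events and any worsening of a baseline diagnosis from AE and SAE reporting with no general exception for suspected relation to the IMP, so no causality assessment is required for them

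*Protocol*

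**What the plan says.** Protocol 9.2.1 opens its list with: "The following events are frequent in care homes and will not be reported as AEs or SAEs". The list includes sepsis, venous thromboembolism, heart failure, hypotension, hypoglycaemia, non-COVID respiratory failure and suicide. Its last bullet is a catch-all: "Any event listed in the IMP appendices". The text after the list extends the exemption to existing conditions: "Similarly, diagnoses present at baseline (including any worsening of that condition) and known comorbidities will not be reported". It then adds: "If any of the above lead to hospitalisation or death, then they will comprise part of the primary outcome".

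Sections 9.2 and 9.4.1 tell care home staff to report SAEs except those that 9.2.1 removes. Section 9.4.2 places the causality judgement downstream of that report: "On receipt of an SAE, seriousness and causality will be determined independently by the PI".

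The opening text of section 9 gives a second channel: "Serious adverse events, hospitalisation and death will all be reported in real time via the trial database for review by the relevant principal investigator". The same sentence sends these events to the medical adjudicator and the DMC. Section 9 also has side effects entered weekly, keeps expedited reporting for related serious events not expected under the RSI, and lets an IMP appendix add requirements. Section 14.9 has event adjudicators review outcome events as well as SAEs.

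**The concern.** A resident who enters with heart failure, diabetes or a history of clots may suffer a drug harm that looks like a worsening of that condition. Section 9.2.1 tells staff not to report such an event, however serious it is and whether or not the drug is suspected. The first decision lies with care home staff, and Protocol 1.2.1.1 says that 72% of care homes have no registered healthcare professionals in their core staffing.

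At stake are the SAR and SUSAR summaries in SAP 8.1 and the expedited reporting in Protocol 9.5. Both depend on an individual judgement of relatedness. If that judgement is not asked for when the event happens, it is hard to recover later from routine data.

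**Working it through.** No power or sample size figure bears on this point. The check is a count of the list and a comparison of sections.

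**Count of the 9.2.1 list**
- Bullets: 28, of which one is the catch-all, so 28 − 1 = 27 named events.
- Named events limited by reference to trial medication: 2. One is the bullet opening "Allergic reaction (not related to trial medication"; the other is "Medication (non-trial) error".
- Named events with no such limit: 27 − 2 = 25.

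The allergic-reaction bullet shows that the drafters had a form of words for an exception. It was not used for any other clinical event on the list, or for worsening baseline diagnoses.

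**Path of an exempt event, by how serious it is**

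| Event | Route to the PI | Is relatedness required to be recorded? |
|---|---|---|
| Serious, not on the list and not a baseline condition | SAE form (9.2, 9.4.2) | Yes (9.4.2) |
| Exempt, leads to admission or death | Real-time review (section 9) | Not stated; 9.2.1 assigns it to the primary outcome |
| Exempt, life-threatening, disabling or medically important, managed in the home | None required | No |

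For the third row, staff may contact the study team for advice (1.2.1.1), and section 14.7 has the PI ensure that a potential SAE is submitted once informed of it. Both depend on someone treating as an SAE what 9.2.1 says not to report.

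**Whether the other provisions supply the missing step**
- *Adjudicators (14.9).* Part of the primary outcome, SUSAR and SAR are listed as alternatives. The SUSAR category leaves out outcomes and expected events listed in the protocol or appendices. The power to raise an event to SAR is given for SAEs. Section 9.7 describes the adjudicators as blinded and their task as a consistency review.
- *Safety endpoint (2.2).* SARs are counted excluding primary and secondary outcomes, so admissions and deaths drop out a second time.
- *Weekly side effects (section 9).* Section 9.1 says that events expected under 9.2.1 are not reported, and the two are not reconciled.
- *IMP appendices.* Section 9 says they may add requirements. The catch-all bullet makes listing an event there a reason not to report it, whereas 9.1 and SAP 8.2 require the events pre-specified there to be collected.
- *Expectedness.* Section 9 and 9.5.1 use the RSI. Section 9.4.2 names the RSI and then the protocol's own expected events. Section 14.9 uses the protocol and appendices.

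None of these requires a relatedness judgement for an exempt event.

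**The case against.** The strongest reply is that the trial has other ways to see harm. Deaths and admissions go to the PI, the adjudicator and the DMC. All-cause death and admission are the top two levels of the primary outcome, and time to each is compared by arm. Cause-specific admission and mortality are tabulated, and SAP section 3 gives the DMC by-arm safety data and between-group estimates. Pre-specified adverse events are collected in every arm. The IMP appendices, which are not among the documents, may tighten reporting for a given drug.

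Most of this stands, and it rules out two stronger readings. A reader might infer that exempt harms can never be classed as SARs or SUSARs and that the safety record would look clean whatever the drug did. The documents do not support that: PI and adjudicator review of deaths and admissions could identify a reaction, and an excess of either would appear in the randomised comparison.

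A reader might also take the plan's control rates as the size of the gap: (10% + 15%) × 3,200 = 800 residents per arm, with 3,200 = 6,400 / 2. That counts outcome events, not unassessed harms. These are the events section 9 already sends for review. They include COVID-19 events, run to 60 days although minimum SAE reporting (9.3) ends with treatment (42 days in 1.2.4), and in the standard care arm involve no IMP.

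The reply does not fill the gap itself. Comparisons between arms do not replace individual expedited reporting, and the review in section 9 asks for no relatedness judgement.

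**Conclusion.** The point holds as a gap in required assessment. For 25 named events with no trial-medication limit, the catch-all and any worsening of a baseline diagnosis, the plan requires no causality judgement even when the event is serious and the drug is suspected. The gap is plainest for serious events managed in the home. For admissions and deaths the sections conflict: review is required, but recording relatedness is not. SAR and SUSAR counts can therefore be too low, and section 9's own duty to expedite related, unexpected serious events can be missed by staff who follow 9.2.1 exactly.

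The number of events affected cannot be derived from the documents, which give no rate for exempt serious events and no prevalence of baseline diagnoses. The conclusion rests on the master protocol as written and assumes that no IMP appendix restores the missing step. It should be settled before an IMP is opened.

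**What to change.** 1. Add to 9.2.1: *The exemption does not apply to any event meeting the SAE definition in section 9.2 that care home staff, the GP or the PI suspects may be related to the IMP; such events follow sections 9.4.2 and 9.5.* Staff and GP need to be named, because a PI cannot suspect an event that is never reported. Using the full 9.2 definition covers disabling and medically important events managed in the home.
2. Add a yes/no field for relatedness, completed by the PI at the real-time review of deaths and hospitalisations in IMP homes.
3. Reconcile sections 9, 9.1, 9.2.1, 9.4.2 and 14.9. State whether expectedness is judged against the RSI or the protocol's list, and whether an outcome event can be a SUSAR. Settle the catch-all bullet against the collection of pre-specified events in 9.1.

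The cost is protocol wording, one form field and slightly more PI time per event. As a rough guide to the workload of item 2 at full recruitment over 60 days, the control rates give 800 residents in the IMP arm if the drug has no effect. Reading the design odds ratio of 0.67 as applying to admission or death, the odds are 0.67 × 0.25/0.75 = 0.2233, the risk is 0.2233/1.2233 = 18.3%, and the count is about 584. Section 9 already sends these events to the PI, so the addition is one answer at each review.
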